In both Studies M14-867 and M14-868, in all subjects with baseline ALT elevations, the ALT levels showed a trend toward normal or became normal with DAA treatment, and there have been no on-treatment ALT elevations above baseline. The ALT normalization pattern was similar across all arms (i.e., both ABT-493 and ABT-530 dose levels) in both studies. Other laboratory abnormalities were infrequent and were primarily associated with well-described hemolytic effect of RBV, manifesting as Grade 1 anemia in total of 4 subjects, all occurring in Study M14-868 RBV-containing arms. Observed total bilirubin elevations were Grade 1 or 2 with predominantly indirect fraction, were mostly isolated occurrences, and normalized or stabilized with continued DAA therapy. Total bilirubin elevations were primarily observed in the RBV-containing arms.

The safety of the combination regimen of ABT-493 and ABT-530 in subjects with compensated cirrhosis is investigated in Study M14-867 Part 2 (ABT-493/ABT-530 [200 mg/120 mg] QD for 12 weeks) and Study M14-868 Part 2 (ABT-493/ABT-530 [300 mg/120 mg] QD for 12 weeks with and without ribavirin or for 16 weeks without ribavirin). Based on 82 subjects with compensated cirrhosis enrolled in these arms who have received 4 weeks or more of treatment, the ABT-493 and ABT-530 regimen has demonstrated a favorable safety profile in this patient population. The majority of adverse events have been Grade 1 or 2 and there have been no treatment discontinuations.

A detailed discussion of the preclinical pharmacology and toxicology, in vitro virology and metabolism, and clinical data for ABT-493, ABT-530 and the combination of ABT-493 and ABT-530 can be found in the ABT-493 and ABT-530 Fixed-Dose Combination Investigator's Brochure.

AbbVie evaluated the combination of ABT-493 (300 mg QD) + ABT-530 (120 mg QD) in healthy Western subjects in Phase 1 drug-drug interaction (DDI) studies and in Han Chinese, Japanese and Caucasians in Study M15-432. Based on cross-study comparison, the exposures ( $C_{max}$  and  $AUC_{24}$ ) in Japanese and Han Chinese subjects were comparable to the exposures observed in Western subjects. Overall, results from these studies demonstrate similar pharmacokinetic profiles between Han Chinese and Caucasian subjects and support parallel approach in the proposed China development strategy utilizing the Global Phase 3 dose.

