eGFR (C-MDRD)	< LLN – 60 mL/min/1.73 m ²	< 60 – 30 mL/min/1.73 m ²	< 30 – 15 mL/min/1.73 m ²	< 15 mL/min/1.73 m ²
Cholesterol	> ULN – 7.75 mmol/L	> 7.75 – 10.34 mmol/L	> 10.34 – 12.92 mmol/L	> 12.92 mmol/L
Albumin	< LLN – 30 g/L	< 30 – 20 g/L	< 20 g/L	--
Lymphocyte	< LLN – 0.8 × 10 ⁹ /L	< 0.8 – 0.5 × 10 ⁹ /L	< 0.5 – 0.2 × 10 ⁹ /L	< 0.2 × 10 ⁹ /L
aPTT	> ULN – 1.5 × ULN	> 1.5 – 2.5 × ULN	> 2.5 × ULN	--
Sodium (low)	< LLN – 130 mmol/L	--	< 130 – 120 mmol/L	< 120 mmol/L
Sodium (high)	> ULN – 150 mmol/L	> 150 – 155 mmol/L	> 155 – 160 mmol/L	> 160 mmol/L
Potassium (low)	< LLN – 3.0 mmol/L	--	< 3.0 – 2.5 mmol/L	< 2.5 mmol/L
Potassium (high)	> ULN – 5.5 mmol/L	> 5.5 – 6.0 mmol/L	> 6.0 – 7.0 mmol/L	> 7.0 mmol/L

Table 15. Definitions of Toxicity Grades 1, 2, 3, and 4 for Laboratory Values (Continued)

Test	Grade 1	Grade 2	Grade 3	Grade 4
Triglycerides	> 1.71 – 3.42 mmol/L	> 3.42 – 5.7 mmol/L	> 5.7 – 11.4 mmol/L	> 11.4 mmol/L
Magnesium (low)	< LLN – 0.5 mmol/L	< 0.5 – 0.4 mmol/L	< 0.4 – 0.3 mmol/L	< 0.3 mmol/L
Magnesium (high)	> ULN – 1.23 mmol/L	--	> 1.23 – 3.30 mmol/L	> 3.30 mmol/L
CPK	> ULN – 2.5 × ULN	> 2.5 – 5 × ULN	> 5 – 10 × ULN	> 10 × ULN

Assessments of hepatotoxicity will be made based on a single laboratory parameter collected at any post-baseline visit through the Final Treatment visit using the following criteria:

- ALT > 5 × ULN and $\geq 2 \times$ baseline;
- Total bilirubin $\geq 2 \times$ ULN and > baseline;
- Total bilirubin $\geq 2 \times$ ULN and > baseline and direct/total bilirubin ratio > 0.4;
- Increase from nadir by grade in ALT:
 - ALT > 3 – 5 × ULN (Grade 2);
 - > 5 – 20 × ULN (Grade 3);
 - > 20 × ULN (Grade 4).

The direct/total bilirubin ratio will be calculated using the same date/time sample corresponding to the total bilirubin elevation. For the summary of increase from nadir by grade in ALT, the post-baseline value must represent an increase from the first nadir (including baseline) to be counted, where the grade of the post-baseline value must be more extreme than the grade of the nadir value. First nadir is defined as the last value prior to the first increase. The maximum ratio relative to the ULN will be used to determine if subjects meet the criteria listed above.

Assessments of hepatotoxicity will also be made based on multiple laboratory parameters collected at any post-baseline visit through the Final Treatment visit using the following criterion:

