Hematology and chemistry data values will be categorized as low, normal, or high based on the normal ranges of the laboratory used for each sample. Shift tables from baseline to minimum value and from baseline to maximum value during the DB and OL Treatment Periods will be created for each treatment arm. The shift tables will cross-tabulate the frequency of subjects with baseline values below/within/above the normal range versus minimum/maximum post-baseline values below/within/above the normal range.

The laboratory parameters listed in [Table 15](#) will be categorized according to the toxicity grades defined in the table. The number and percentage of subjects with a maximum toxicity grade of 1, 2, 3 or 4 during treatment (DB treatment and OL treatment summarized separately) will be calculated for each treatment arm. To be counted, the post-baseline value must have a toxicity grade that is more extreme than the toxicity grade corresponding to the baseline value. For each laboratory parameter in [Table 15](#), the summary will also include the number and percentage of subjects with a maximum of at least Grade 3 for each treatment arm. For summaries of data collected during the DB Treatment Period, the difference in rates between the 2 arms (Arm A minus Arm B), and

the 2-sided 95% CI for the rate difference using the Wilson score method for a difference in proportions will be presented.¹² These summaries will also be presented for the set of HCV/HIV co-infected subjects (determined at Screening) within the populations/groups specified in Section 11.1.

A listing of all relevant laboratory parameters will be provided for each subject who had an increase to Grade 2 or higher for any laboratory variable in Table 15.

For the assessments of hepatotoxicity based on single and multiple laboratory parameters, the number and percentage of subjects meeting the criterion during treatment will be calculated for each criterion. A listing of all ALT, AST, total, indirect and direct bilirubin, ratio of direct to total bilirubin, and alkaline phosphatase values will be provided for each subject who met any of the single or multiple criteria defined above. The listings will be reviewed to assess bilirubin (e.g., mixed or direct predominance) and temporal relationships for subjects with $ALT > 3 \times ULN$ (or ALT Grade 2+) and total bilirubin $\geq 2 \times ULN$.

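### Read literally, the SAP tests the direct/total bilirubin criterion only at the peak total-bilirubin sample, so its count can be too low but never too high

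*SAP*

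**What the plan says.** SAP 11.3.1 introduces the single-parameter criteria this way: "Assessments of hepatotoxicity will be made based on a single laboratory parameter collected at any post-baseline visit through the Final Treatment visit". Two of them use total bilirubin. One needs a value of at least 2 × ULN that is above baseline. The other adds the direct fraction: "> baseline and direct/total bilirubin ratio > 0.4". This second one is called the direct-fraction criterion below.

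The paragraph after the list fixes which sample supplies the fraction: "The direct/total bilirubin ratio will be calculated using the same date/time sample corresponding to the total bilirubin elevation". After some text on the ALT nadir, it closes with "The maximum ratio relative to the ULN will be used to determine if subjects meet the criteria listed above".

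SAP 11.3.2 says what is reported: "the number and percentage of subjects meeting the criterion during treatment will be calculated for each criterion". It also plans a listing of ALT, AST, bilirubin fractions, the direct/total ratio and alkaline phosphatase "for each subject who met any of the single or multiple criteria defined above". The stated review of that listing for mixed or direct predominance is limited to subjects who also have ALT above 3 × ULN (or Grade 2 or higher) together with total bilirubin of at least 2 × ULN.

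**The concern.** Using the maximum is a safe shortcut when a criterion gets easier to meet as the value rises. That is true of a threshold on total bilirubin alone. It is not true of the direct-fraction criterion, because the sample with the highest total bilirubin need not be the one with the highest direct fraction. The closing sentence applies the maximum to the whole list, so a programmer following it would look at the peak sample, read the ratio there and stop.

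What is at stake is one safety count: subjects whose raised total bilirubin comes with a substantial direct fraction. Counts of this kind tend to be small, so a single missed subject would be visible. The stated listing review would not necessarily recover such a subject, because it covers only those who also have the ALT elevation.

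**Working it through.** The plan states no figure to reproduce. The check compares two ways of applying the direct-fraction criterion: at the sample with the maximum total bilirubin/ULN (the literal reading), or at every post-baseline sample. One ULN per subject is assumed.

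**1. A worked record (invented values).** Baseline total bilirubin is 0.8 × ULN.

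| Post-baseline sample | Total bilirubin (× ULN) | Direct/total | ≥ 2 × ULN | > baseline | Ratio > 0.4 |
|---|---|---|---|---|---|
| 1 | 1.2 | 0.20 | no | yes | no |
| 2 (peak) | 3.0 | 0.20 | yes | yes | no |
| 3 | 2.2 | 0.50 | yes | yes | yes |
| 4 | 1.0 | 0.20 | no | yes | no |

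At the peak the criterion fails on the ratio, so the subject is not counted. Sample 3 meets all three parts, so the any-sample rule counts the subject. The criterion on total bilirubin alone is met under both rules.

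**2. Direction of the error.**
- If the peak sample qualifies, some sample qualifies, so the peak rule can never count a subject that the any-sample rule does not.
- If a non-peak sample qualifies, the peak is at least as high, so it is also at least 2 × ULN and above baseline. A missed subject therefore always meets the criterion on total bilirubin alone.

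**3. Check on 100,000 synthetic subjects with four samples each.** The values were drawn only to test the logic and say nothing about frequency.

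| Criterion | Any-sample and peak rules disagree |
|---|---|
| ALT > 5 × ULN and ≥ 2 × baseline | 0 |
| Total bilirubin ≥ 2 × ULN and > baseline | 0 |
| Direct-fraction: any-sample yes, peak no | 21,018 |
| Direct-fraction: peak yes, any-sample no | 0 |

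**4. Illustrative miss rate.** Suppose a subject has k samples at or above 2 × ULN and above baseline, and each has a ratio above 0.4 with probability p, independently of the other samples and of the size of the elevation. The any-sample rule counts the subject with probability 1 − (1 − p)^k, and the peak rule with probability p. The share missed is 1 − p / [1 − (1 − p)^k].

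| k | p = 0.2 | p = 0.5 |
|---|---|---|
| 2 | 1 − 0.2/0.36 = 44% | 1 − 0.5/0.75 = 33% |
| 3 | 1 − 0.2/0.488 = 59% | 1 − 0.5/0.875 = 43% |
| 4 | 1 − 0.2/0.5904 = 66% | 1 − 0.5/0.9375 = 47% |

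Both p and k are assumed. With k = 1 nothing is missed. If the direct fraction persists within a subject, the share falls toward zero. If the largest elevations tend to be the indirect ones, it rises. An 8-week subject has four scheduled on-treatment visits (Weeks 1, 2, 4 and 8), so without unscheduled draws k = 4 needs every one of them to be elevated.

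**The case against.** The strongest reply is that the peak-only reading is not forced. The criteria draw on any post-baseline visit, and the ratio is tied to the sample with the elevation, not to the maximum. The direct/total ratio is also not a ratio to the ULN, so the closing sentence could be taken to govern only the ULN part. This reading is possible. It leaves the closing sentence at odds with the direct-fraction criterion, though, because that sentence covers the whole list without exception. Either way the text needs the same clarification.

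The second reply is that nobody disappears from view. That stands. A missed subject is counted on total bilirubin alone and is listed with the direct/total ratio.

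Three stronger readings are tempting, and the documents support none of them.

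- A reader might infer that this is the only count separating direct from indirect elevation. SAP 11.3.1 lists direct and indirect bilirubin as separate chemistry variables, and SAP 11.3.2 plans baseline-to-maximum shift tables for chemistry data, plus mean changes and plots for direct bilirubin. A qualifying sample has direct bilirubin above 0.4 × 2 = 0.8 times the total-bilirubin ULN. That would appear as a shift to high if the direct-bilirubin ULN is lower than this, a limit the documents do not give. What this criterion alone does is count a total-bilirubin elevation together with its direct fraction.
- A reader might infer that an indirect peak hiding a direct rise is the expected pattern, because the protocol introduction reports "Observed total bilirubin elevations were Grade 1 or 2 with predominantly indirect fraction". The same passage says those Phase 2 elevations were mostly isolated, normalized or stabilized on treatment, and occurred mainly in ribavirin arms. This trial gives no ribavirin, and isolated elevations argue against repeated samples at 2 × ULN.
- A reader might take the 33% to 66% range as an estimate for this trial. It rests on assumed inputs and on independence within a subject.

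**Conclusion.** The point holds as a defect in a derivation rule. Under the literal wording, the direct-fraction count can be too low and cannot be too high. The effect is limited to that one count and its percentage, and probably to few or no subjects, since it needs at least two samples at or above 2 × ULN with the higher one at a ratio of 0.4 or less. The size cannot be stated more closely, because the documents give no data on how often this occurs. No efficacy result is touched. The conclusion rests on reading the maximum-ratio sentence as covering every listed criterion, which is what it says. If an any-sample rule was intended, the remaining problem is wording that contradicts that intent.

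**What to change.** In SAP 11.3.1, state that the direct-fraction criterion is met if any one post-baseline sample through the Final Treatment visit has total bilirubin of at least 2 × ULN, total bilirubin above baseline, and a direct/total ratio above 0.4, all in that same sample. Limit the maximum-ratio sentence to the other criteria.

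The cost is one added sentence, one qualified sentence and a small programming change. The data are already collected and already listed. The count can only stay the same or rise.

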#### **5.2.2 Exclusion Criteria**

A subject will not be eligible for study participation if he/she meets any of the following criteria:

1. Female subject who is pregnant, breastfeeding or is considering becoming pregnant during the study or for approximately 30 days after the last dose of study drug.
2. Recent (within 6 months prior to study drug administration) history of drug or alcohol abuse that could preclude adherence to the protocol in the opinion of the investigator.

3. Positive test result at Screening for hepatitis B surface antigen (HBsAg) or hepatitis B virus (HBV) DNA > LLOQ if HBsAg is negative.
4. HCV genotype performed during screening indicating co-infection with more than one HCV genotype.
5. Requirement for and inability to safely discontinue contraindicated medications or supplements listed in [Table 1](#) at least 2 weeks or 10 half-lives (whichever is longer) prior to the first dose of any study drug.
6. Clinically significant abnormalities, other than HCV infection or HCV/HIV co-infection, based upon the results of a medical history, physical examination, vital signs, laboratory profile, and a 12-lead electrocardiogram (ECG) that make the subject an unsuitable candidate for this study in the opinion of the investigator, including, but not limited to:
  - Uncontrolled diabetes as defined by a glycated hemoglobin (hemoglobin A1C) level > 8.5% at the Screening Visit.
  - Active or suspected malignancy or history of malignancy (other than basal cell skin cancer or cervical carcinoma in situ) in the past 5 years.
  - Uncontrolled cardiac, respiratory, gastrointestinal, hematologic, neurologic, psychiatric, or other medical disease or disorder, which is unrelated to the existing HCV infection.
7. Any cause of liver disease other than chronic HCV-infection, including but not limited to the following:
  - Hemochromatosis
  - Alpha-1 antitrypsin deficiency
  - Wilson's disease
  - Autoimmune hepatitis
  - Alcoholic liver disease
  - Steatohepatitis on liver biopsy considered to be the primary cause of the liver disease rather than concomitant/incidental with HCV infection

8. Screening laboratory analyses showing any of the following abnormal laboratory results:
- ALT > 10 × upper limit of normal (ULN)
  - AST > 10 × ULN

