#### **6.1.7.1 Management of Increases in ALT**

If a subject experiences a post-baseline increase in ALT to  $> 5 \times \text{ULN}$  which is also  $> 2 \times$  the baseline value, the subject should have a confirmatory ALT measurement performed.

If the ALT increase is confirmed to be  $> 5 \times \text{ULN}$  which is also  $2 \times$  the baseline value, the recommendations below should be followed:

- Complete hepatic questionnaire; evaluate for alternate etiology of ALT elevation; document in the source, update the medical history and concomitant medications eCRF (if applicable), and obtain additional testing as appropriate (e.g., hepatitis B panel, etc.).
- Manage the subject as medically appropriate.
- Repeat ALT, AST, total and fractionated bilirubin, alkaline phosphatase and INR within 1 week. Repeat liver chemistries as indicated until resolution.
- Discontinue study drugs if any of the following is observed at any time:
  - ALT level is  $\geq 20 \times$  ULN in the absence of an alternate etiology.
  - Increasing direct bilirubin or INR or onset of symptoms/signs of hepatitis.
  - At the discretion of the investigator.

Alternate management of ALT increases is permitted with approval of the AbbVie TA MD.

During the DB Treatment Period, if confirmed ALT values meet or exceed predefined toxicity thresholds, refer to Section 5.1.2.

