- ALT > 3 × ULN (Grade 2 + and increase from nadir grade) and total bilirubin ≥ 2 × ULN.

For the criterion based on multiple laboratory parameters, the analysis will check to see if the subject meets the ALT and total bilirubin portions of the criterion at any time within the Treatment Period (i.e., draw dates do not need to be concurrent). The maximum ratio relative to the ULN for each parameter will be used to determine if the subject meets the criterion listed above. For ALT, the post-baseline value must represent an increase from the first nadir (including baseline) to be counted. First nadir is defined as the last value prior to the first increase. The grade of the post-baseline ALT value must be at least Grade 2 and more extreme than the grade of the nadir value. For total bilirubin, a subject or event will be counted if the post-baseline laboratory values meet the above criteria regardless of the baseline laboratory value (i.e., the post-baseline laboratory value does not need to be worse than the baseline laboratory value).

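### The only combined ALT/bilirubin count in the SAP leaves out an ALT rise that stays within Grade 3; a supplementary count without the nadir-grade condition would show it

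*SAP*

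**What the plan says.** SAP section 11.3.1 has one criterion that combines two liver parameters: "ALT > 3 × ULN (Grade 2 + and increase from nadir grade) and total bilirubin ≥ 2 × ULN". The text below it repeats the condition on ALT: "The grade of the post-baseline ALT value must be at least Grade 2 and more extreme than the grade of the nadir value". On the nadir it says: "First nadir is defined as the last value prior to the first increase", with baseline included. Each parameter enters at its maximum ratio to ULN, the ALT and bilirubin draws need not coincide, and bilirubin counts whatever its baseline value.

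The grade bands come from Table 15 and the single-parameter list in the same section. Grade 2 ALT is > 3 to 5 × ULN, the next band is "> 5 – 20 × ULN (Grade 3"), and Grade 4 is above 20 × ULN.

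The single-parameter criteria in 11.3.1 are:
- ALT > 5 × ULN and ≥ 2 × baseline;
- total bilirubin ≥ 2 × ULN and above baseline, and the same with a direct/total ratio above 0.4;
- an ALT increase from nadir by grade, with the same condition: "where the grade of the post-baseline value must be more extreme than the grade of the nadir value".

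SAP section 11.3.2 tabulates a number and percentage for each criterion and lists the liver tests of every subject who meets any of them. It has those listings reviewed for subjects with ALT > 3 × ULN (or Grade 2+) and total bilirubin ≥ 2 × ULN. It attaches no nadir condition to that review.

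In protocol section 5.2.2, criterion 8, the ALT limit for exclusion is "ALT > 10 × upper limit of normal (ULN") at screening.

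**The concern.** The grade step makes the size of ALT rise needed depend on where the nadir lies within its band. Grade 3 is wide: its upper limit is four times its lower limit. A subject who starts in Grade 3, triples ALT and develops raised bilirubin does not enter the combined count.

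This count is the only place where the plan tabulates ALT and bilirubin elevation in the same subject. Safety is part of the primary objective and very few such cases are expected, so one omission can be the difference between 0 and 1 in an arm. The tabulated set can also differ from the set that SAP 11.3.2 names for review, because the review set carries no nadir condition.

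**Working it through.** The plan states no figure to reproduce here. The check applies the written rules to example series. The ALT and bilirubin values are illustrations, in multiples of ULN.

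**Inputs.** Grade bands: SAP Table 15. Nadir, maximum and grade-step rules: SAP 11.3.1. Eligibility: protocol 5.2.2, criterion 8.

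**Step 1: can the nadir be Grade 3?** Only screening ALT above 10 × ULN is excluded, so > 5 to 10 × ULN is eligible. That range lies in Grade 3.

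**Step 2: rise needed from a Grade 3 nadir.** The maximum must exceed 20 × ULN, so the fold rise must exceed 20 / nadir:
- nadir 5.1: 20/5.1 = 3.92
- nadir 6: 20/6 = 3.33
- nadir 8: 20/8 = 2.50
- nadir 10: 20/10 = 2.00

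The limiting value is 20/5 = 4.0. By contrast, a nadir of 4.9 (Grade 2) reaches Grade 3 at 5.1, a rise of 5.1/4.9 − 1 = 4.1%.

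**Step 3: series through the criteria.** TB is total bilirubin, baseline then maximum.

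| ALT series | TB | Max/nadir | Max/baseline | Grade, nadir to max | Combined | ALT > 5 and ≥ 2 × baseline | TB ≥ 2 and > baseline |
|---|---|---|---|---|---|---|---|
| 6, 18 | 0.8, 3 | 3.00 | 3.00 | 3 to 3 | no | yes | yes |
| 5.1, 20.0 | 0.8, 3 | 3.92 | 3.92 | 3 to 3 | no | yes | yes |
| 5.1, 20.1 | 0.8, 3 | 3.94 | 3.94 | 3 to 4 | yes | yes | yes |
| 4.9, 5.1 | 0.8, 3 | 1.04 | 1.04 | 2 to 3 | yes | no | yes |
| 9.9, 5.1, 19.7 | 0.8, 3 | 3.86 | 1.99 | 3 to 3 | no | no | yes |
| 9.9, 5.1, 19.7 | 3, 3 | 3.86 | 1.99 | 3 to 3 | no | no | no |

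In the first two rows the subject is missing from the combined count but present in both single-parameter rows, and so is listed. In the fifth row only bilirubin brings the subject into the listing.

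In the last row nothing does. The ALT-by-grade row also fails (Grade 3 to Grade 3), and the bilirubin rows need a value above baseline. Such a baseline is possible under the protocol, because criterion 8 limits direct and not total bilirubin.

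**The case against.** The other side has four good points.

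- **The typical subject is not lost.** For ALT 6 to 18 × ULN with a new bilirubin rise, the ALT and bilirubin rows both count the subject, the full liver profile is listed, and the review in SAP 11.3.2 looks for this combination. Bilirubin would usually also move up a grade in the maximum-grade table. SAP 11.3.2 has a further listing, for any subject with an increase to Grade 2 or higher in any Table 15 variable. A reader might infer that the SAP misses such subjects altogether; apart from the narrow exception, it does not. This stands.
- **The rule is deliberate.** The grade step is stated for both ALT nadir criteria, and SAP 12.1, item 18, says the hepatotoxicity analysis was added to align with the development programme. The row is correct for its own definition. That is a reason not to replace it. It is no reason against a second row beside it.
- **The event should be uncommon.** Protocol section 3.0 reports that, in the Phase 2 studies, raised baseline ALT moved toward normal on treatment, with no on-treatment elevations above baseline. This stands for active drug. It says nothing about placebo, where a Grade 3 nadir is more likely to persist.
- **Stopping at 20 × ULN does not strengthen the point.** Protocol 6.1.7.1 lists ALT ≥ 20 × "ULN in the absence of an alternate etiology" among reasons to discontinue study drug. A reader might infer that values above 20 × ULN will seldom be observed, so that a Grade 3 nadir can hardly ever qualify. That does not follow. The value that triggers stopping is itself an on-treatment value and is counted, and SAP 6.1.2 keeps values up to 2 days after the last dose.

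**Conclusion.** The point holds for the combined count. As written, the count omits ALT rises of up to just under 4-fold that begin and end in Grade 3, even with total bilirubin ≥ 2 × ULN. In most such cases the single-parameter rows and the reviewed listing still show the subject. The exception is a fall then a rise within Grade 3 that stays below 2 × baseline, with bilirubin no higher than an already raised baseline. That subject meets no hepatotoxicity criterion and does not enter the hepatotoxicity listing.

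The number affected is probably small. It requires a first nadir above 5 × ULN, a later rise that does not pass 20 × ULN, and bilirubin ≥ 2 × ULN. The documents do not give the share of subjects with baseline ALT in Grade 3. Even that share would count subjects who could be exposed to the rule and not subjects omitted by it, so no figure is offered.

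This is a coarse rule with an avoidable gap in one safety row. It is not a contradiction in the plan.

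**What to change.** Keep the criterion in SAP 11.3.1 as it is. Add to the same table, by arm for the double-blind period and separately for the open-label period:

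1. the number and percentage of subjects with post-baseline ALT > 3 × ULN and total bilirubin ≥ 2 × ULN, without the nadir-grade condition, which is the combination SAP 11.3.2 already names for review;
2. a sub-row for those whose maximum ALT is also ≥ 2 × the first nadir.

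Extend the hepatotoxicity listing in SAP 11.3.2 to every subject in row 1, so that the last series in the table above is listed and reviewed.

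All six example series enter row 1. All except 4.9 to 5.1 × ULN enter the sub-row, at 3.00, 3.92, 3.94, 3.86 and 3.86 times nadir. The change does not remove small grade crossings from the existing combined row; 4.9 to 5.1 × ULN with raised bilirubin would still be counted there.

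The cost is one or two table rows and the matching programming, from data already collected. The downside is that row 1 will include some subjects whose ALT was already raised at baseline and did not worsen. The sub-row is there to separate them.
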